#### *10.1.2.4 Objective response rate*

The objective response rate is defined as the percentage of patients with measurable disease who achieve an objective response by RECIST1.1 criteria (i.e. Complete response or Partial Response) to rucaparib.

We will estimate the objective response rate, along with the exact 95% confidence interval, for the population of patients.

### *10.1.3 Analysis of exploratory endpoints*

#### *10.1.3.1. Estimate the percentage of patients with a loss-of-function mutation or total allelic loss of second (somatic) gene allele (i.e. biallelic inactivation):*

The DNA mutations present in the tumor will be identified through Foundation Medicine sequencing. Patients with a somatic alteration including: protein truncating mutations, splice site mutations, homozygous deletions, large protein truncating rearrangements, and deleterious missense alterations in the pre-specified gene list (*BRCA1, BRCA2, ATM, CHEK2, NBN, BRIP1, RAD50, RAD51C, RAD51D, PALB2, MRE11, FANCA, FANCB, FANCC, FANCD2, FANCE, FANCF, FANCG, FANCI, FANCL, FANCM*) will be considered biomarker positive. For biomarker positive and biomarker negative subjects, we will calculate PSA50 response rates with confidence intervals for hypothesis generation.

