Objectives	Primary

To estimate the PSA50 response rate to rucaparib in patients with metastatic and non-metastatic prostate cancer that harbor an inactivating mutation in a homologous recombination DNA repair gene while on treatment with rucaparib, defined as a decline in PSA to 50% of baseline level, confirmed with a second measurement at least 4 weeks apart (PCWG3).

Secondary

- To estimate the median PSA progression-free survival (PCWG3).
- To estimate the median progression-free survival (PCWG3).
- To estimate the objective response rate (ORR) in those patients with measurable disease.
- To determine the safety/tolerability of rucaparib in a population of men with hormone sensitive prostate cancer.

Correlatives/Tertiary

- To measure the quantitative change in gamma-H2AX, RAD51, 53BP1 formation in tumor tissue following treatment with rucaparib (M1 disease only).
- To develop an RNA expression signature associated with response to rucaparib (M1 disease only).
- To estimate the percentage of patients with a loss-of-function mutation or total allelic loss of second somatic gene allele (i.e. LOH, or biallelic inactivation) (In all patients undergoing biopsy or with archived tissue).
- To investigate any association between PARP-1 and PARP-2 protein and mRNA expression levels in tumor with response to rucaparib (In all patients undergoing biopsy or with archived tissue).
- To examine the incidence of reversion mutations in circulating tumor DNA at clinical progression.

[figure not shown]

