### Exploratory Endpoints

- PSA50 response, defined as decline in PSA to ≥50% of baseline level, confirmed with a second measurement at least 4 weeks later, in patients with and without a loss-of-function mutation or total allelic loss of second (somatic) gene allele (i.e. biallelic inactivation) (In patients who undergo biopsy or with archival tissue available).
- To associate PSA response to rucaparib with changes in gamma-H2AX, RAD51, 53BP1 formation in tumor tissue compared to baseline (In M1 patients who undergo biopsy).
- To associate mRNA expression array signature with PSA response (In M1 patients only who undergo biopsy).
- To associate PSA response to rucaparib with baseline PARP-1 and PARP-2 protein and mRNA expression levels in baseline tumor biopsy specimens or archived tissue.
- To associate the incidence of reversion mutations with clinical progression.

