### Exploratory Analyses

*Estimate the percentage of patients with a loss-of-function mutation or total allelic loss of second (somatic) gene allele (i.e. biallelic inactivation):*

The DNA mutations present in the tumor will be identified through Foundation Medicine sequencing. Patients with biallelic inactivation in an HRD gene(BRCA1, BRCA2, ATM, CHEK2, NBN, BRIP1, RAD50, RAD51C, RAD51D, PALB2, MRE11, FANCA, FANCB, FANCC, FANCD2, FANCE, FANCF, FANCG, FANCI, FANCL, FANCM) will be considered biomarker positive. For biomarker positive and biomarker negative subjects, we will calculate PSA50 response rates with confidence intervals for hypothesis generation.

*mRNA expression profile signature (positive and negative) and PSA50 response rates:*  
Subjects will have pretreatment tumor (or archived tissue) tested with mRNA expression profiling and scored for likelihood for response to rucaparib per the Decipher GRID platform (GenomeDx). For subjects considered to have a positive mRNA expression signature based upon a binary score assigned via the GenomeDx proprietary algorithm, a PSA50 response rate will be calculated. Similarly, a calculation will be performed for subjects considered to have a negative sRNA expression signature.

*PARP-1, PARP-2, γH2AX, RAD51, 53BP1 mRNA/protein levels:*

In patients that have biopsy-able disease, subjects will have pretreatment and on-treatment tumor biopsy specimens analyzed. IHC and RNA in situ hybridization staining

PARP-1 and PARP-2 will be performed on the pretreatment samples and scored on scale of 0 (none) to 3 (intense staining), and the results will be associated with responses for both proteins, separately, using descriptive statistics and Fisher's Exact Tests.

Immunofluorescence will be used to quantify the median intensity of each gH2AX, RAD51m and 53BP1 foci per cell as well determine the median number of foci per cell on the pretreatment biopsies. Using analytical microscopy, Drs. [name] and [name] have developed imaging software, which can isolate single nuclei and quantify both the intensity and number of immunofluorescent foci per nucleus (i.e. per cell). Using FFPE tissue obtained at biopsy, we will examine the change in DNA damage foci number and intensity (reported as median percent change) induced by PARPi in PSA50 responders versus non-responders using a T-test.

*Reversion Mutations:*

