### 1.3 Rationale

#### 1.3.1 Rationale for conducting the study

Much of the early work studying mechanism of action and efficacy of PARPi has been done in ovarian and breast cancer due to the well-characterized incidence of BRCA1/2 mutations in these cancers. However, somatic mutations in DNA-repair genes have been identified in both primary(9) and metastatic castration-resistant prostate cancer (mCRPC)(10), with prevalence rates of approximately 5-10% in localized prostate cancer and 20-25% in metastatic castration-resistant prostate cancer (mCRPC).

These findings served as the rationale to test PARPi (olaparib) in heavily pre-treated mCRPC (TOPARP-A trial, Mateo et al., NEJM 2015).(1) Although the presence of a DNA-repair defect in the tumor was not an eligibility requirement, the response rate to olaparib was 33% in the unselected population (16 of 49; 95% CI 20-48%), including a PSA decline of over 50% (PSA50) in 10/49 patients. The trial did identify somatic and germline mutations in DNA-repair genes, and the presence of a DNA-repair defect correlated with improved response rates (88% vs. 6%) as well as improved progression-free (9.8 vs. 2.7 months) and overall (13.8 vs. 7.5 months) survival compared to DNA-repair proficient cancers. Notably, all 7 patients with a BRCA2 mutation achieved a PSA50 response and 4/5 patients with an ATM mutation had a clinical response to olaparib. The most pronounced responses were observed in those patients with germline, inactivating mutations in BRCA2, most of which also had somatic loss-of-heterozygosity of the second allele in the tumor. Several studies are now ongoing to confirm PARPi as a potential treatment strategy for mCRPC either as a single agent (NCT01682772) or in combination with next-generation hormonal therapies (NCT01576172, NCT02500901). The FDA recently announced breakthrough designation for olaparib in patients with mCRPC refractory to novel hormonal therapy, with germline or somatic mutations in BRCA1/2 or ATM.

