### *1.3.3 Rationale for correlative studies*

#### *1.3.3.1 Genetic mutation analysis in tumor*

We hypothesize that inactivation or loss of the second allele in the gene of interest (i.e. homologous recombination gene with germline mutation) is required for response to PARPi. Tumors will be analyzed using the FoundationOne platform by Foundation Medicine (Cambridge, MA). This test sequences provides mutation analysis in 315 selected genes and rearrangement analysis in 28 genes. The genes include those commonly mutated (*BRCA2, ATM, BRCA1*, etc.). The analysis provides a depth of coverage of 500X, and is reported by variant analysis with regard to likely pathogenicity. By cataloging the mutations present in the primary tumors for subjects in the study, correlative analysis associating response with specific mutations can be performed. The testing will be inclusive of a sub-panel of genes of particular interest (*BRCA1, BRCA2, ATM, CHEK2, NBN, BRIP1, RAD50, RAD51C, RAD51D, PALB2, MRE11, FANCA, FANCB, FANCC, FANCD2, FANCE, FANCF, FANCG, FANCI, FANCL, and FANCM*). We will also collect and examine ctDNA before treatment and at progression. Reversion mutations are a known mechanism of resistance to PARP inhibitors, which may give insight into the etiology of clinical progression while on rucaparib in this clinical setting.

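### Section 10.1.3.1 makes any listed somatic alteration biomarker-positive, with no second hit required and LOH not named, while its own heading and the synopsis define the marker as biallelic inactivation.

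*Combined protocol and SAP*

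**What the plan says.** The target is stated consistently.

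- The heading of Section 10.1.3.1 asks for the percentage of patients with a loss-of-function mutation or "total allelic loss of second (somatic) gene allele (i.e. biallelic inactivation".
- The synopsis objective on the same marker names LOH: "total allelic loss of second somatic gene allele (i.e. LOH, or biallelic inactivation".
- The synopsis exploratory endpoint compares PSA50 response "in patients with and without a loss-of-function mutation or total allelic loss of second (somatic) gene allele (i.e. biallelic inactivation".
- Section 1.3.3.1 gives the hypothesis behind it: "inactivation or loss of the second allele in the gene of interest (i.e. homologous recombination gene with germline mutation) is required for response" to a PARP inhibitor.

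The rule for assigning patients to groups is stated twice, and the two statements differ.

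- Synopsis, Exploratory Analyses: "Patients with biallelic inactivation in an HRD gene" are biomarker positive.
- Section 10.1.3.1: "Patients with a somatic alteration including: protein truncating mutations, splice site mutations, homozygous deletions, large protein truncating rearrangements", together with deleterious missense changes, in any of the listed genes, are biomarker positive.

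In both places the analysis is PSA50 rates with confidence intervals in the positive and negative groups, described as hypothesis-generating. No test is specified.

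**The concern.** The statistical section is where an analyst looks for the operative rule, and its rule does not define the quantity in its heading. It counts alterations of given types. It does not ask whether both copies of one gene are lost.

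Two kinds of patient are affected. The first is a man enrolled on a single somatic mutation whose other allele is intact. The second is a germline carrier whose tumour has lost the normal allele through LOH, with no further listed mutation. The second kind matters because Section 1.3.1, describing the olaparib study, says the most pronounced responses were in germline BRCA2 carriers, "most of which also had somatic loss-of-heterozygosity of the second allele in the tumor".

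Two results are at stake: the estimated percentage with biallelic inactivation, and the PSA50 comparison meant to inform the second-allele hypothesis. The trial is open-label and single-arm. With two definitions on file, the choice between them could also be made after the PSA results are known.

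**Working it through.** The documents state no sample size, power or expected rate for this analysis, so there is no figure to reproduce. The check is a comparison of the rules, followed by an illustration on assumed inputs.

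**Step 1. Apply each rule to the possible tumour types.** Eligibility (synopsis and Section 3.3) accepts one pathogenic mutation, and the synopsis states that it may be germline or somatic, so all five types below can be enrolled.

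| Tumour | Synopsis rule | 10.1.3.1, list closed | 10.1.3.1, list open (LOH counts) |
|---|---|---|---|
| Germline mutation + listed somatic hit, same gene | positive | positive | positive |
| Germline mutation + LOH only | positive | **negative** | positive |
| Germline mutation, second allele intact, no listed somatic alteration | negative | negative | negative |
| Somatic, both alleles lost | positive | positive | positive |
| Single listed somatic hit, second allele intact | negative | **positive** | **positive** |

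The last row is misgrouped on both readings of the list. The second row is misgrouped only if the list is closed. The open reading adds a difficulty of its own: nothing in the rule ties the alteration to the gene carrying the first hit, so LOH or a mutation in some other listed gene would also make a patient positive.

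**Step 2. How large could this be?** Every input here is an assumption, except that the total of 28 is borrowed from the two-stage design in Section 10.

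- g: germline share, 0.3 to 0.7.
- L: biallelic by LOH among germline carriers, 0.3 to 0.7.
- M: biallelic by a listed somatic second hit among germline carriers, 0.1 to 0.2.
- B: biallelic among somatic-only tumours, 0.5 to 0.8.
- PSA50: 75% if biallelic, 25% if not, a true difference of 50 points.
- All 28 tumours evaluable, with no unrelated alterations in other listed genes.

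Take g = 0.5, L = 0.5, M = 0.2, B = 0.8. The shares of all patients are: germline + LOH 0.25; germline + listed hit 0.10; germline, intact allele 0.15; somatic biallelic 0.40; somatic single hit 0.10. The true biallelic share is 0.25 + 0.10 + 0.40 = 0.75, or 21 of 28.

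*Closed list.*
- Positive share = 0.10 + 0.40 + 0.10 = 0.60, against a true 0.75.
- PSA50, positive = (0.50 × 0.75 + 0.10 × 0.25) / 0.60 = 67%.
- PSA50, negative = (0.25 × 0.75 + 0.15 × 0.25) / 0.40 = 56%.
- Apparent difference: about 10 points instead of 50. Of the 21 biallelic patients, 0.25 × 28 = 7 are scored negative.

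*Open list.*
- Positive share = 0.75 + 0.10 = 0.85.
- PSA50, positive = (0.75 × 0.75 + 0.10 × 0.25) / 0.85 = 69%; negative = 25%.
- Apparent difference: 44 points.

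I repeated these formulas over 18 combinations: g = 0.3, 0.5, 0.7; (L, M) = (0.3, 0.2), (0.5, 0.2), (0.7, 0.1); B = 0.5, 0.8. The closed list gives apparent differences from −13 to +24 points, and the open list from +29 to +47.

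The distortion therefore depends mainly on which reading the analyst takes, and the documents do not settle that.

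**The case against.** The strongest reply is that the right rule is already in the protocol. The synopsis says biallelic inactivation, and the Section 10.1.3.1 list opens with a word that need not make it exhaustive. LOH in a tumour can be called a somatic alteration, and the heading directly above names allelic loss. Section 1.3.3.1 frames the hypothesis around genes with a germline mutation; for a germline carrier, a listed somatic alteration in the same gene is a second hit, so the rule makes sense there.

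Much of this stands, and it rules out several stronger readings.

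- A reader might infer that germline-plus-LOH tumours *are* scored negative. The text does not settle that; it follows only from the closed reading.
- A reader might infer that the marker has become somatic versus germline origin. It has not: germline carriers with a listed second hit are positive under both rules.
- A reader might infer that a hypothesis test is invalid. None is planned; the analysis is descriptive.

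The reply does not rescue the rule. The single-somatic-hit error remains on either reading of the list, eligibility admits such patients, and the two sections still assign them to opposite groups.

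It is also fair that the comparison will be imprecise in any case. The synopsis limits this endpoint to patients with biopsy or archived tissue, so fewer than 28 may contribute.

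**Conclusion.** Wrong as written, in an exploratory analysis. The firm defect is two conflicting definitions of biomarker-positive, of which the one in Section 10.1.3.1 does not match its own heading, the synopsis or the hypothesis in Section 1.3.3.1. Single-hit somatic patients with an intact second allele are misgrouped whether the list is open or closed. Germline-plus-LOH patients are misgrouped only if it is closed.

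The size cannot be computed from the documents, which give no germline share, LOH share or PSA50 rate by zygosity. The illustration shows only that the effect could be small or large. A reader might conclude that the contrast would be driven to zero or reversed. That happens only for some assumed inputs under the closed reading, and the documents do not support stating it as the expected result.

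The primary endpoint, the two-stage design, its type I error and its power do not depend on this classification.

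**What to change.** Use the synopsis rule in both places, spelled out as follows.

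- **Positive:** two inactivating hits in the same listed gene, that is, a germline or somatic pathogenic variant plus either a second somatic hit or LOH of the wild-type allele; or homozygous deletion of a listed gene.
- **Negative:** a single hit with the second allele retained.
- **Not evaluable:** zygosity or LOH cannot be called from the sequencing report. These tumours should be counted and reported separately, not placed in the negative group.

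State how LOH is called, and settle the definition before PSA50 results are compared by group.

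The cost is a wording change, with two caveats. Some tumours will move to not evaluable, which reduces an already small analysis set. And Section 1.3.3.1 describes the assay as mutation analysis in 315 genes and rearrangement analysis in 28, without mentioning an LOH or zygosity call, so the plan must confirm that the report supports one.

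### The exploratory biallelic analysis pools 21 genes into two crude PSA50 rates, so the difference between them may be confounded by gene

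*Combined protocol and SAP*

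**What the plan says.** Section 1.3.3.1 gives the hypothesis behind the analysis: "We hypothesize that inactivation or loss of the second allele in the gene of interest" is required for response to PARP inhibition. The planned output in section 10.1.3.1 is: "For biomarker positive and biomarker negative subjects, we will calculate PSA50 response rates with confidence intervals for hypothesis generation". The synopsis (Exploratory Analyses) plans the same output.

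Both places pool the same 21 genes, but they define the marker differently. The synopsis counts as positive "Patients with biallelic inactivation in an HRD gene". Section 10.1.3.1 counts a somatic alteration from a list that ends "homozygous deletions, large protein truncating rearrangements, and deleterious missense alterations in the pre-specified gene list". That list does not name loss of heterozygosity and does not ask for two hits in the same gene.

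Neither place stratifies by gene, restricts to BRCA1/2 or adjusts. Section 1.3.3.1 adds that "correlative analysis associating response with specific mutations can be performed", but section 10 contains no such analysis.

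On the cited olaparib trial, section 1.3.1 reports that "all 7 patients with a BRCA2 mutation achieved a PSA 50 response", that 4 of 5 ATM patients had a clinical response, and: "The most pronounced responses were observed in those patients with germline, inactivating mutations in BRCA2, most of which also had somatic loss-of-heterozygosity".

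**The concern.** The contrast is meant to inform whether a second hit matters. If BRCA1/2 tumours respond more often than tumours with other mutations, and also carry a second hit more often, the positive group will contain more BRCA1/2 men. It will then show a higher PSA50 rate even if second-allele status has no effect within any gene. This holds even for a perfectly classified marker.

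The plan already treats gene as important, since it caps enrolment of the other gene groups at 10 of 30. Looking at response by gene alone would not solve the problem, because it again varies one factor while ignoring the other.

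What is at stake is the hypothesis carried into the next trial, for example selecting patients on second-allele status when gene was the driver. A bias in the opposite direction could hide a real second-hit effect.

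**Working it through.** **Plan's own figures.** The documents give no figure for this analysis. The Simon design in section 10 (12 patients, stop at 6 or fewer; 28 in total, 18 or more needed) reproduces: early stopping 0.613 under 50% (stated 0.61), power 0.902 (stated 90%), attained one-sided type I error 0.081 (limit 0.1). None of this depends on the biomarker analysis.

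**Inputs from the documents.** Up to 30 men, at most 10 of them outside the capped gene group (section 10; section 3.2; synopsis).

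**Assumptions, not in the documents.** All 30 have usable tissue, split as 20 BRCA1/2 and 10 other. PSA50 is pB in BRCA1/2 and pO in the others, whatever the biallelic status. Biallelic loss is qB and qO.

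**Formulas.**
- Expected PSA50 in positives = (20·qB·pB + 10·qO·pO) / (20·qB + 10·qO)
- Expected PSA50 in negatives = (20·(1−qB)·pB + 10·(1−qO)·pO) / (20·(1−qB) + 10·(1−qO))

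**Illustration:** pB = 80%, pO = 20%, qB = 80%, qO = 30%.
- Positives: (16 × 0.8 + 3 × 0.2) / 19 = 13.4 / 19 = 70.5%
- Negatives: (4 × 0.8 + 7 × 0.2) / 11 = 4.6 / 11 = 41.8%
- Gap: +28.7 points, with no second-hit effect in either gene group

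**Equal biallelic rates:** same PSA50 rates, qB = qO = 50%.
- Positives: (10 × 0.8 + 5 × 0.2) / 15 = 60%
- Negatives: the same, 60%
- Gap: 0

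**Loss commoner in the other genes:** same PSA50 rates, qB = 40%, qO = 80%.
- Positives: (8 × 0.8 + 8 × 0.2) / 16 = 8 / 16 = 50.0%
- Negatives: (12 × 0.8 + 2 × 0.2) / 14 = 10 / 14 = 71.4%
- Gap: −21.4 points

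If PSA50 does not differ by gene, the gap is also zero. With PSA50 of 70–80% v 20–40% and biallelic loss of 70–90% v 20–40%, it runs from 8 to 42 points. That grid contains only cases with loss commoner in BRCA1/2, so it is not a full range.

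**What the planned output would show.** The plan has two rates with intervals and no test. In simulations of the illustration, an observed gap of at least 20 points favouring the positive group appeared in about 70% of trials. The two 95% intervals failed to overlap in only about 6%. In a similar case (PSA50 75% v 25%, biallelic loss 80% v 20%), a typical result is 13/18 (95% CI 47–90%) against 5/12 (15–72%).

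**Within gene group.** The expected spurious gap is zero under these assumptions, but precision is poor. With 80% biallelic loss the 20 BRCA1/2 men split 16 and 4. At 75% response that gives 12/16 (95% CI 48–93%) against 3/4 (19–99%).

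**The case against.** The strongest objection is that the documents do not establish the bias. Section 1.3.1 says only that most of the best-responding germline BRCA2 men had loss of heterozygosity. It gives no biallelic rate for any other gene, and the 4 of 5 ATM responses do not suggest a large gap between ATM and BRCA2. The definition in section 10.1.3.1 adds doubt: read literally, a germline BRCA2 carrier whose second hit is loss of heterozygosity could be classed negative, which would push the bias against the hypothesis. The synopsis would class him positive, and the word introducing the list leaves it unclear whether the list is complete. This stands. A reader might infer that a BRCA-driven response will appear as support for the second-hit hypothesis; the documents do not support so firm a statement.

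A reader might also want to express the risk as a false-positive rate from a pooled Fisher test. Section 10.1.3.1 plans no such test; Fisher's test is planned for PARP-1 and PARP-2 staining.

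The analysis is also labelled hypothesis-generating, section 10.2.1 bars subanalyses from supporting efficacy conclusions, and pooling does not bias the percentage with biallelic inactivation, which the section's title names. This limits the consequence. It does not make the pooled contrast interpretable, and a confounded contrast can still generate the wrong hypothesis.

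Lastly, stratification cannot settle the question. Assuming a real effect (80% v 40% in BRCA1/2, 50% v 20% in the others), an exact stratified test would detect it in about 32% of trials with 20 and 10 men, and in about 20% with 13 and 7. This also stands: a stratified estimate should not be presented as the decisive test of the hypothesis.

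**Conclusion.** The point holds as a risk of confounding, of unknown size and direction. The pooled PSA50 difference mixes gene with second-allele status, and nothing in the plan separates them. Under the stated assumptions, a gap of about 29 points (70.5% v 41.8%) can arise with no second-hit effect. Under other assumptions equally open on the documents, the gap is zero or about 21 points the other way. All of these figures rest on assumed response and biallelic rates by gene and on 30 men with usable tissue. The synopsis limits the analysis to men with a biopsy or archival tissue, so 30 is a ceiling. The matter is confined to an exploratory analysis; the primary endpoint and its decision rule stand.

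**What to change.** 1. Reconcile the gene grouping. Under Expected enrollment the synopsis counts ATM with BRCA1/2 in the group of at least 20; the synopsis sample-size text, section 3.2 and the overall cap in section 10 do not. Section 10's stage 1 cap again groups ATM with BRCA1/2.
2. Reconcile the two definitions of biomarker positive, stating whether loss of heterozygosity counts and whether both hits must be in the same gene.
3. In section 10.1.3.1 and the synopsis, also report PSA50 with exact 95% confidence intervals by biallelic status within BRCA1/2 and within the other genes.
4. Add a gene-stratified odds ratio with 95% confidence interval, labelled descriptive and hypothesis-generating.
5. Keep the pooled rates, with a statement that their difference is not adjusted for gene.

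The cost is a wording change and a few table rows, with no new data. The drawback is small cells and wide intervals, and a gene group in which all men share one biallelic status contributes nothing to the stratified estimate. Two strata also leave differences among the individual genes within each group unadjusted.
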